2 INTRODUCTION

[figure not shown]
2.1 Study Rationale

MK-1167 is a PAM of the α 7 nAChR and is not considered a compound with high potential for risk of harm to participants [European Medicines Agency 2017]. MK-1167 is not a biological molecule, does not exhibit species-specific action, and is not directed towards

The purpose of this study is to evaluate the safety and tolerability, and effect of multiple doses of donepezil on the multiple dose PK of MK-1167 in patients with AD. Donepezil is an AChEI, and 10 mg daily is the standard of care for patients with mild to moderate AD.

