|----------|-----------------------|--------------------------|-------------------------|----------------------------|--|--------------|
| Panel A | MK-1167 | 5 MG, 1 MG | 6 MG | Oral | loading doses QD Days 1 to 7 | Test Product |
| Panel A | MK-1167 | 1 MG | 3 MG | Oral | maintenance doses QD Days 8 to 21 | Test Product |
| Panel A | Donepezil | 10 MG | 10 MG | Oral | QD dosing during entire treatment period | Comparator |
| Panel A | Placebo to MK1167 | 0 MG | All Dosage Levels | Oral | QD Days 1 to 21 | Placebo |
| Panel B | MK-1167 | 5 MG, 1 MG | 6 mg | Oral | QD Days 1 to 31 | Test Product |
| Panel B | Donepezil | 10 MG | 10 mg | Oral | QD dosing during entire treatment period | Comparator |
| Panel B | Placebo to MK-1167 | 0 MG | All Dosage Levels | Oral | QD Days 1 to 31 | Placebo |

| Total Number of Intervention Groups/Arms | There will be 2 panels (A and B). Panel A will have approximately 16 participants, and Panel B will have approximately 12 participants. |
|--|--|
| Duration of Participation | Each participant will participate in the study for approximately 11 weeks for Panel A and 12 weeks for Panel B from the time the participant provides documented informed consent through the final protocol-specified contact. After a screening period of up to 4 weeks, each participant will be receiving assigned study intervention for approximately 21 days for Panel A and 31 days for Panel B. |

Study Governance Committees:

| Executive Oversight Committee | No | | | | | |
|------------------------------------|----|--|--|--|--|--|
| External Data Monitoring Committee | No | | | | | |
| Clinical Adjudication Committee | No | | | | | |

Study Accepts Healthy Participants: No

A list of abbreviations is in Appendix 13.

08X3SB

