Study MK-1167-004 was a randomized, placebo-controlled, single-site, double-blind study of MK-1167 in 2 panels of healthy elderly male and female participants, conducted in conformance with GCP. The primary objective of the study was to assess the safety, tolerability, and to characterize the PK of multiple doses of MK-1167 in healthy elderly study participants before administration in patients with AD in later studies. In this study, approximately 8 participants received single-day oral loading doses of MK-1167 10 mg/PBO following by maintenance doses of oral doses of MK-1167 1 mg/PBO daily for 16 days (Panel A), and approximately 8 participants received multiple-day oral loading doses of MK-1167 10 mg/PBO for 3 days following by maintenance doses of oral doses of MK-1167 3 mg/PBO daily for 13 days (Panel B). This study is clinically complete, but DBL has not yet been achieved. A total of 16 participants were enrolled in this study, all of whom received multiple oral doses of MK-1167/PBO. Preliminary data indicate that the multiple-dose administration of MK-1167/PBO was generally well tolerated in healthy male and female elderly study participants. Of the 8 participants in Panel A, 5 (62.5%) experienced 1 or more AEs during the study. The most frequently reported AE (>1 participants) after

both panels were mild to moderate in intensity.

There were no serious AEs, ECIs or deaths reported in the study and no participant discontinued from the study due to an AE. There were no clinically meaningful trends observed as a function of study intervention for laboratory safety tests, VS, or ECGs.

MK-1167-006 (PN006)

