3 HYPOTHESES, OBJECTIVES, AND ENDPOINTS

Hypotheses are aligned with objectives in the Objectives and Endpoints table.

The study population consists of patients with mild to moderate AD, 50 to 90 years of age.

| Primary Objective | Primary Endpoint |
|---|--|
| Evaluate the safety and tolerability of MK-1167 when administered to patients with mild to moderate Alzheimer's Disease on stable doses of oral donepezil 10 mg daily | Adverse events, discontinuation due to Adverse events |
| Secondary Objectives | Secondary Endpoints |
| Evaluate the pharmacokinetic profile of MK-1167 when administered to patients with mild to moderate Alzheimer's Disease on stable doses of oral donepezil 10 mg daily Estimation: | AUC0-24, Cmax, C24, Tmax, CL/F, Vz/F, t1/2 |
| Tertiary/Exploratory Objectives | Tertiary/Exploratory Endpoints |
| Evaluate the changes in cognitive function of Alzheimer's Disease patients by comparing the Mini Mental State Examination and Digit Symbol Substitution Test scores obtained at baseline with those from the last day of dosing. | Mini Mental State Examination scores Digit Symbol Substitution Test scores |
| CCI | Germline genetic variation |
| Explore the relationships between genetic variation, response to the treatment(s) administered, and mechanisms of disease. Variation across the human genome may be analyzed for association with clinical data collected in the study. | Germline genetic variation |

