4.2.1.2 Pharmacokinetic Endpoints

A secondary objective of this study is to evaluate the plasma PK profile of MK-1167 following multiple doses in male and female participants with AD. To characterize the PK of MK-1167, plasma AUC0-24, Cmax, and C24 will be determined. Other PK endpoints to be evaluated include Tmax, apparent terminal t1/2, apparent CL/F, and apparent Vz/F.

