5.1 Inclusion Criteria

An individual is eligible for inclusion in the study if the individual meets all of the following criteria:

Type of Participant and Disease Characteristics

- 1. Be in good health based on medical history, physical examination, VS measurements, and ECGs performed before randomization.
 - a. Participants with chronic medical conditions, including but not limited to hypertension, hyperlipidemia, diabetes (Type 1 or 2) or hypothyroidism, which have been well-controlled on a stable dose of medication for the past 2 months and who are not receiving any proscribed medications for treatment may be enrolled if clinically acceptable to the investigator and Sponsor.
 - Appendix 9 provides a table of the 12-Lead Electrocardiogram Evaluation Criteria.
- 2. Be in good health based on laboratory safety tests obtained at the Screening Visit. Appendix 2 provides a table of laboratory safety tests to be performed. Appendix 10 provides an algorithm for the assessment of out-of-range laboratory values.
- 3. BMI between 18 and 35 kg/m², inclusive. See Section 8.3.1 for criteria on rounding to the nearest whole number. BMI = weight (kg)/height (m)².
- 4. Report a history of cognitive and functional decline with gradual onset and slow progression for at least 1 year before Screening, that is either corroborated by an informant who knows the subject well or is documented in medical records.
- 5. Meet the criteria for a diagnosis of probable AD based on NINCDS-ADRDA criteria for probable AD (Appendix 11).
- 6. Have a MMSE-2 score between 14 and 28, inclusive, at Screening as confirmed by the investigator. The MMSE-2 should be administered by a certified practitioner alternating the colors (red, blue) of the exam for a given subject to avoid learning effects with repeated administration.
- 7. Be receiving donepezil 10 mg daily for symptomatic treatment of cognitive impairment associated with AD. The dose level must be stable for at least 2 months prior to Screening. If receiving donepezil via a transdermal system (ie, patch), it should be a 10-mg/day dose and should switch prescription to a 10-mg oral daily dose, before enrollment.

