6.3 Measures to Minimize Bias: Randomization and Blinding

6.3.1 Intervention Assignment

Participants will be assigned randomly according to a computer-generated allocation schedule.

The sample allocation tables are provided below in Table 4 and Table 5.

Table 4 Allocation of Participants to Treatment For Panel A

| Number of Participants | Days 1 to 7 | Days 8 to 21 |
|------------------------|--------------------|-----------------------------|
| | Treatment | Treatment |
| n=12 | 6-mg MK-1167 QD + | 3-mg MK-1167 QD + donepezil |
| | donepezil | |
| n=4 | Placebo to MK-1167 | Placebo to MK-1167 |
| | + donepezil | + donepezil |

n=number of participants in a subset of the study; OD=once daily.

The suggested doses may be adjusted downward based on evaluation of safety, tolerability and/or pharmacokinetic data observed in previous treatment periods/panels.

Note: Female participants will be assigned the low allocation range and male participants will be assigned the upper allocation range

Table 5 Allocation of Participants to Treatment For Panel B

| Number of Participants | Days 1 to 31 |
|------------------------|-----------------------------|
| | Treatment |
| n=9 | 6-mg MK-1167 QD + donepezil |
| n=3 | Placebo to MK-1167 |
| | + donepezil |

n=number of participants in a subset of the study; QD=once daily.

The suggested doses may be adjusted downward based on evaluation of safety, tolerability and/or pharmacokinetic data observed in previous treatment periods/panels.

Note: Female participants will be assigned the low allocation range and male participants will be assigned the upper allocation range

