9.2 Hypotheses/Estimation

Objectives and hypotheses of the study are stated in Section 3 of the protocol.

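### Does Section 2.1 commit the trial to estimating donepezil's effect on MK-1167 pharmacokinetics, which its design cannot do?

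*Combined protocol and SAP*

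**What the plan says.** Section 2.1 (Study Rationale) describes the aim as to "evaluate the safety and tolerability, and effect of multiple doses of donepezil on the multiple dose PK of MK-1167 in patients with AD".

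The operative sections say something narrower. Section 9.2 states: "Objectives and hypotheses of the study are stated in Section 3 of the protocol". The secondary objective in Section 3 begins "Evaluate the pharmacokinetic profile of MK-1167 when administered to patients with mild to moderate" and goes on to specify Alzheimer's disease on stable oral donepezil 10 mg. Section 4.2.1.2 follows suit: "To characterize the PK of MK-1167, plasma AUC0-24, Cmax, and C24 will be determined". Section 9.3.2 lists only plasma MK-1167 variables.

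Donepezil is universal. Inclusion criterion 7 requires participants to "Be receiving donepezil 10 mg daily for symptomatic treatment of cognitive impairment associated with AD", at a dose stable for at least 2 months before Screening. The synopsis gives the donepezil regimen in both panels as "QD dosing during entire treatment period". In Table 5 the active cell is "6-mg MK-1167 QD + donepezil". Table 4 has the same pairing, and the placebo cells carry donepezil too.

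Donepezil itself is sampled before and during MK-1167 dosing (Schedule of Activities; Appendix 8). The 24-hour samples are assayed and the rest archived. The readable endpoint lists in Sections 3, 4.2.1.2, 9.3.2 and 9.3.3 contain no donepezil variable. Some text is masked or missing: after the Estimation label in Section 3, one exploratory objective, much of 4.2, part of 9.5.1 and the content of 9.8.

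**The concern.** A stated purpose should be answerable by the design. Donepezil's effect on MK-1167 pharmacokinetics is a contrast between two conditions, MK-1167 with donepezil and MK-1167 alone, and only the first occurs here. A reader who stops at Section 2.1 could expect an interaction estimate in the study report, or could take the MK-1167 profile on donepezil as evidence about an interaction that was never tested. That would matter because Section 2.2.4 names CYP3A4 as one of donepezil's metabolic routes, and Section 4.3 treats co-administration of MK-1167 with moderate CYP3A4 inhibitors as relevant to the dose.

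A second worry points the other way. The plan draws donepezil samples that could show whether MK-1167 changes donepezil exposure, yet no readable endpoint uses them.

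**Working it through.** **1. Is the effect named in Section 2.1 estimable?**

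Count of participants by treatment, from Tables 4 and 5:

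| | MK-1167 + donepezil | MK-1167 without donepezil | Placebo + donepezil |
|---|---|---|---|
| Panel A | 12 | 0 | 4 |
| Panel B | 9 | 0 | 3 |
| Total | 21 | 0 | 7 |

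The row totals 12 + 4 = 16 and 9 + 3 = 12 match the panel sizes in the synopsis. Placebo participants yield no MK-1167 concentrations, so only the 21 count.

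For a log PK parameter, write

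y = b0 + b1·(Panel B) + b2·(late day) + b3·(Panel B × late day) + b4·(donepezil) + participant effect + error.

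The two-day layout is illustrative. With 21 participants and two days there are 42 rows and 5 columns. The donepezil column is 1 in every row, so it equals the intercept. The matrix has rank 4, not 5, and b4 is not estimable. More participants would not help. If some recipients were off donepezil, the rank would be 5.

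**2. Does any planned analysis need that effect?**

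| Place | What it asks for | Needs MK-1167 without donepezil? |
|---|---|---|
| 2.1 | Donepezil's effect on MK-1167 PK | Yes |
| Title; 4.1 | Safety, tolerability and PK on stable donepezil | No |
| 3 | MK-1167 PK profile on stable donepezil | No |
| 4.2.1.2; 9.3.2 | MK-1167 PK parameters | No |
| 9.5.1, readable text | Geometric means by day; accumulation ratios Day 8/Day 1 and Day 21/Day 1 | No |

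The sample code in 9.5.1 has day as the fixed effect and participant as the random effect. It has no donepezil term and no term for external data. Section 2.1 stands alone, and Section 9.2 points to Section 3 for the objectives.

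**3. The reverse contrast, MK-1167 on donepezil**

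This one is estimable: donepezil is measured without MK-1167 (11 draws) and with it (10 draws), and a with/without model has rank 2 of 2. Of the 11 earlier draws, 8 fall at 0.5 to 12 hours, leaving 11 − 8 = 3 at 24 hours. That is an inference from draw counts, because the assay days cannot be read.

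A rough precision can be given only on an assumed within-participant CV, which the documents do not supply. Take 15% to 30%, m = 3 independent baseline values and one on-treatment value:

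- s² = ln(1 + CV²), which is 0.0223 to 0.0862
- v = s²·(1 + 1/m), which is 0.0297 to 0.1149
- 90% CI factor = exp[t(0.95, n − 1)·√(v/n)]

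For n = 12 and CV 30%: exp(1.796 × √(0.1149/12)) = exp(0.176) = 1.19.

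| Group | n | Factor (×/÷), CV 15% to 30% |
|---|---|---|
| Panel A active | 12 | 1.09 to 1.19 |
| Panel B active | 9 | 1.11 to 1.23 |
| Panel A placebo | 4 | 1.22 to 1.49 |
| Panel B placebo | 3 | 1.34 to 1.77 |

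If the three baselines are worth only one (m = 1), the active ranges widen to 1.12 to 1.24 and 1.14 to 1.29. These figures also assume no dropout. The synopsis plans for 12 evaluable completers out of about 16 in Panel A. If that is the panel total and the 3:1 ratio holds, Panel A would have 9 active and 3 placebo completers, and so the Panel B precision.

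**The case for a change.** The strongest case for acting is that the contradiction is real, does not depend on masked text and costs one sentence to remove. No hidden analysis can create an MK-1167 observation off donepezil. The 5 mg donepezil dechallenge supply mentioned in the summary of changes would give only unplanned, non-randomised variation, still on donepezil. And 2.1 is the section that announces the study's purpose. All of this stands as a description of the wording.

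It does not make the plan defective. The analysts work from Sections 3 and 9, which agree with each other and with the design. Nor is it certain that the clause in 2.1 is idle. Section 4.3 already uses donepezil-free data from PN001, PN002 and PN004 Panel A to project exposures. Masked text could set the new results beside earlier studies. PN004 Panel B, for instance, had healthy elderly participants on "maintenance doses of oral doses of MK-1167 3 mg/PBO daily for 13 days (Panel B"), the same maintenance dose as Panel A here. Such a comparison would be confounded by population and loading regimen, but it would be one way to pursue the clause, so insisting that it be deleted would go beyond what the readable text supports.

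On the donepezil samples, it is fair to say that drawing 21 of them with no readable endpoint invites a question. But the Schedule of Activities says which are assayed and which archived, and Section 8.6 leaves to the Sponsor the decision on which samples are measured. No readable objective asks for MK-1167's effect on donepezil, and an endpoint may sit in the masked text.

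**Conclusion.** No change to the plan is needed. The observation is correct: 0 of 21 planned MK-1167 recipients are without donepezil, so the trial's own data cannot isolate the effect that 2.1 names. It amounts to a clerical inconsistency in a background sentence. Section 3 governs, its readable pharmacokinetic objective is answerable, and following Sections 3 and 9 as written gives the same endpoints, estimates and intervals whether or not 2.1 is reworded. The effect on the primary and secondary results is nil.

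The reverse contrast would be an optional exploratory addition. Its precision depends on an assumed CV, an inferred number of baselines and full retention, and whether it is already planned cannot be judged from the readable text.

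The conclusion rests on the readable parts of Sections 3, 4.2, 9.5.1 and 9.8. Masked text might add a cross-study comparison, but it could not make the within-trial effect estimable or alter the analyses that can be read.

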2.2 Background

08X3SB

Refer to the IB for detailed background information on MK-1167.

2.2.1 Pharmaceutical and Therapeutic Background

MK-1167 is a PAM of the α 7 nAChR. The compound is being developed for the treatment of cognitive deficits associated with CNS disorders, with a primary focus on AD.

AD is the leading cause of dementia in elderly people and affects an estimated 35 million individuals worldwide, several which is escalating because of increased lifespan. AD is a

progressive neurodegenerative disorder in which cognitive deficits gradually worsen over time. Characteristics of the disease include degeneration of cholinergic neurons in the basal forebrain and reduction of cholinergic innervation of the cerebral cortex, hippocampus, and other regions of the brain.

It has been hypothesized that cholinergic hypofunction contributes to the cognitive deficits of patients suffering from AD. This hypothesis is supported by the fact that AChEIs, which inhibit hydrolysis of ACh, provide symptomatic benefit and have been approved for the treatment of the cognitive impairments in AD. However, AChEIs produce only modest efficacy so a treatment that significantly improves cognition as an adjunctive therapy would represent an important advance.

The $\alpha 7$ nAChR is a ligand-gated ion channel that is highly expressed in brain regions associated with cognitive function. The expression level of $\alpha 7$ nAChRs can be affected by several pathological conditions, including AD. In addition, genetic evidence supports the involvement of the $\alpha 7$ nAChR in cognitive function since both large deletions to Chromosome 15q13.3, as well as smaller deletions to the gene for the $\alpha 7$ nAChR, CHRNA7, frequently produce cognitive deficits in addition to other phenotypes. Positive clinical data in AD patients with $\alpha 7$ nAChR agonists further support the rationale that drugs that enhance $\alpha 7$ nAChR activity have therapeutic potential. Most notably, an $\alpha 7$ nAChR partial agonist, encenicline (Forum Pharmaceuticals, Inc), produced significant effects in a Phase 2 AD study but was discontinued during Phase 3 due to profound GI side effects. These side effects are believed to be due to off-target activity, namely serotonin 5-HT3 receptor antagonism. Furthermore, encenicline, as well as other $\alpha 7$ agonists, cause desensitization of the $\alpha 7$ receptor and produce an inverted U-shaped dose-effect function in a variety of preclinical assays. This profile is thought to limit the efficacy of $\alpha 7$ nAChR agonists and/or require exposures to be in a very specific range to produce efficacy.

PAMs of the α 7 nAChR are hypothesized to exhibit an improved clinical profile in comparison to α 7 nAChR agonists and be devoid of the tolerability issues that halted encenicline. In contrast to α 7 nAChR agonists, PAMs do not promote receptor desensitization. Furthermore, α 7 nAChR PAMs demonstrate efficacy over a much wider range of concentrations in several assays (no inverted U) and maintain efficacy upon repeated dosing. Additionally, α 7 nAChR PAMs exhibit improved selectivity over related channel targets, presumably through binding to a nonconserved region of the α 7 nAChR.

2.2.2 Preclinical and Clinical Studies

Refer to the IB for detailed preclinical studies for MK-1167.

MK-1167-001 (PN001)

08X3SB

Study MK-1167-001 was a randomized, placebo-controlled, double-blind, single ascending dose study to evaluate the safety, tolerability, and PK of MK-1167 in healthy male participants. The study consisted of 4 alternating panels (A, B, C, and D) consisting of 8 participants, each of whom were administered single-oral doses of MK-1167 or placebo (3:1 ratio as an on-site formulation (oral suspension). A total of 32 participants were enrolled, of whom 30 received single-oral doses of MK-1167 (3 to 100 mg). Overall, single-oral doses of MK-1167 up to 76 mg were generally well tolerated in healthy male participants. Of the 32 participants, 28 (87.5%) experienced 1 or more AEs during the study: n=25 (83.3%) on MK-1167 and n=8 (57.1%) on placebo. The most frequently reported AEs (>1 participants) after MK-1167 intervention were headache (11), dizziness (7), fatigue (5), diarrhea, sunburn (4 each), back pain, postural dizziness, gastrointestinal pain, oropharyngeal pain (3 each), dyspepsia, hematoma, skin irritation, and vomiting (2 each). Most AEs were mild to moderate in intensity.

Decreases in orthostatic BP persisted for approximately 5-hours postdose and then resolved spontaneously. No changes to resting BP or HR were observed in this participant, or in any other study participant in semirecumbent testing at any dose. Subsequent doses in the study were adapted such that doses \geq 100 mg were not administered to study participants following the observation of this AE.

There were no serious AEs, ECIs or deaths reported in the study and no participant discontinued from the study due to an AE. There were no clinically meaningful trends observed as a function of study intervention for laboratory safety tests, VS, or ECGs.

MK-1167-002 (PN002)

Study MK-1167-002 was a randomized, placebo-controlled, single site, double-blind study of MK-1167 in healthy participants to assess the safety, tolerability, and PK of multiple doses of MK-1167. This study completed 4 sequential panels (A, B, C, and D) with 8 healthy participants in each panel who received multiple doses of MK-1167 (n=6) or placebo (n=2) in a randomized, blinded fashion. In Panel A, participants received a 4-mg loading dose of MK-1167 or placebo on Day 1 followed by 1 mg maintenance doses every other day on Days 3, 5, 7 and 9. In Panel B, participants received a 20-mg loading dose of MK-1167 or placebo on Day 1 followed by 2 mg QD (maintenance dose) for 9 consecutive days (Days 2 to 10). In Panel C, participants received a 40-mg loading dose of MK-1167 or placebo on Day 1 followed by 4 mg qd (maintenance dose) for 9 consecutive days (Days 2 to 10). In Panel D, participants received a 22-mg loading dose of MK-1167 or placebo qd for Days 1 to 4 followed by 8 mg qd (maintenance dose) starting on Day 5 and for 6 consecutive days.

Based on unblinded data from PN002, single oral loading doses of MK-1167 up to 40 mg and multiple oral doses of MK-1167 (1 to 8 mg) were generally well tolerated in healthy male participants. Of the 32 participants included in the study analysis set, 12 (37.5%) experienced 1 or more AEs during the study: n=10 (41.7%) on MK-1167 and n=2 (25.0%) on placebo. The most frequently reported AE (>1 participant) after MK-1167 intervention was abdominal discomfort (n=3). After placebo intervention, there were no AEs reported by >1 participant. All AEs were mild to moderate in severity, limited in duration, and all resolved without intervention. There were no clinically meaningful trends in laboratory safety measurements, vital signs, physical and neurological examinations, C-SSRS or ECGs. No participant was discontinued or withdrew participation due to an AE.

MK-1167-003 (PN003)

[figure not shown]
08X3SB

Study MK-1167-003 was a single-blind, placebo-controlled, 2-period, fixed sequence investigation of the ability of a single, oral dose of MK-1167 to modify glutamatergic neurotransmission in the prefrontal cortex of healthy adult males using selPOCE-13C-MRS to measure MK-1167 induced changes in the FE of ¹³C-glutamate (¹³C-glu) and ¹³C-glutamine (¹³C-gln) relative to placebo (baseline) treatment. This study is clinically complete and DBL was achieved on 09-MAY-2024. A total of 26 participants were enrolled in this study, of whom 11 received single doses of MK-1167 1 mg and 15 received single doses of MK-1167 6 mg. Overall, single doses of MK-1167 1 mg and 6 mg were generally well tolerated in healthy male participants. Of the 15 participants who received single doses of MK-1167 6 mg, 9 (58%) experienced 1 or more AEs during the study. The most frequently reported AEs (>1 participants) after MK-1167 6 mg intervention were catheter site or venipuncture pain (3) and panic attack (2). The episodes of panic attack were attributed to study-specific procedures in PN003, specifically the requirement in this study to participate in MRS imaging without movement for an extended period of time. All AEs were mild to moderate in intensity and resolved without intervention.

There were no serious AEs, ECIs or deaths reported in the study and no participant discontinued from the study due to an AE. There were no clinically meaningful trends observed as a function of study intervention for laboratory safety tests, VS, or ECGs.

MK-1167-004 (PN004)

Study MK-1167-004 was a randomized, placebo-controlled, single-site, double-blind study of MK-1167 in 2 panels of healthy elderly male and female participants, conducted in conformance with GCP. The primary objective of the study was to assess the safety, tolerability, and to characterize the PK of multiple doses of MK-1167 in healthy elderly study participants before administration in patients with AD in later studies. In this study, approximately 8 participants received single-day oral loading doses of MK-1167 10 mg/PBO following by maintenance doses of oral doses of MK-1167 1 mg/PBO daily for 16 days (Panel A), and approximately 8 participants received multiple-day oral loading doses of MK-1167 10 mg/PBO for 3 days following by maintenance doses of oral doses of MK-1167 3 mg/PBO daily for 13 days (Panel B). This study is clinically complete, but DBL has not yet been achieved. A total of 16 participants were enrolled in this study, all of whom received multiple oral doses of MK-1167/PBO. Preliminary data indicate that the multiple-dose administration of MK-1167/PBO was generally well tolerated in healthy male and female elderly study participants. Of the 8 participants in Panel A, 5 (62.5%) experienced 1 or more AEs during the study. The most frequently reported AE (>1 participants) after

both panels were mild to moderate in intensity.

There were no serious AEs, ECIs or deaths reported in the study and no participant discontinued from the study due to an AE. There were no clinically meaningful trends observed as a function of study intervention for laboratory safety tests, VS, or ECGs.

MK-1167-006 (PN006)

Study MK-1167-006 was an open-label, fixed-sequence, 2-period study to evaluate the safety, tolerability, and PK profile of a single oral dose of MK-1167 coadministered with diltiazem, a calcium channel blocker that has been extensively characterized as an inhibitor of CYP3A4 and frequently used as a perpetrator in DDI studies. The study was performed to assess the effect of MK-1167 on safety, PK, and interaction with CYP3A4 inhibitors in healthy male and female (of non-childbearing potential) study participants prior to introducing the treatment in patients with AD. This study is clinically complete and DBL was achieved on 27-FEB-2024. On Day 1 of Period 1, a single dose of MK-1167 3 mg was administered. PK sampling was performed predose and up to 600 hours postdose. There was a washout of at least 35 days between dosing in Period 1 and the first dose in Period 2. In Period 2, diltiazem was administered QD for 49 consecutive days with a single dose of MK-1167 3 mg coadministered on Day 3. PK sampling for MK-1167 was performed predose and up to 1128 hours post MK-1167 dosing. Predose blood samples were also collected for

diltiazem PK. Safety was monitored throughout the study by repeated clinical and laboratory evaluations.

A total of 16 participants were enrolled in this study, of whom 14 completed the study and received 2 single doses of MK-1167. These participants received a single dose of MK-1167 3 mg alone on Day 1 of Period 1 and a single dose of MK-1167 3 mg coadministered with diltiazem on Day 3 of Period 2. Two participants were discontinued from the study due to AEs (positive COVID-19) on Day -1 of Period 2; these 2 participants received 1 single dose of MK-1167 3 mg alone on Day 1 of Period 1. Overall, single doses of MK-1167 3 mg were generally well tolerated in healthy study participants when administered alone or with diltiazem. Of the 16 study participants, 6 (38%) experienced 1 or more AEs during the study. The most frequently reported AEs (≥2 participants) after MK-1167 intervention were dry mouth, COVID-19, and headache, each reported by 2 (13%) participants. All AEs were mild to moderate in intensity.

There were no serious AEs, ECIs or deaths reported in the study. There were no clinically meaningful trends observed as a function of study intervention for laboratory safety tests, VS, or ECGs.

MK-1167-001, and MK-1167-002 were conducted in Belgium (PN001, PN002) and MK-1167-003 was conducted in the Netherlands (PN003). MK-1167-004 and MK-1167-006 were conducted in the US (PN004, PN006) under the MK-1167 IND.

PK

08X3SB

The PK of MK-1167 in plasma and blood were determined following single oral doses in healthy adult male participants of Given that

the t1/2 estimates were generally equivalent in plasma and blood, these results suggest that the partitioning between the blood and plasma is rapid and reversible. In a comparison of fed and fasted participants following administration of 12-mg MK-1167, the PK exposures in plasma and whole blood were equivalent to one another indicating no relevant food effect on MK-1167 PK.

Additional safety and PK information is available in the IB.

